There are currently no PR services offered to the patients in Georgia. In this context, where resources are limited, yet COPD is a major burden, research is needed to evaluate whether offering PR is feasible and to assess whether the intervention would have similar effects to those observed in other settings. Using a short supervised course, and/or unsupervised home-based exercise is likely to

more economically viable. With limited availability of pharmacotherapy, there is also an opportunity to test the effectiveness of different components of PR or to evaluate a tiered approach tailored to patient need. The findings could have implications for other similar settings.

Objectives

- 1. To tailor the content and delivery of pulmonary rehabilitation to fit the Georgian health service and setting
- 2. Conduct a randomised controlled trial to assess the feasibility of delivering a culturally tailored PR intervention

Study design

A qualitative study and randomised controlled feasibility trial

Methods: Participants, interventions, and outcomes

Phase 1: Tailoring pulmonary rehabilitation to the Georgian context

Study setting

This phase of the project will involve carrying out a qualitative study. The aim will be to carry out three separate focus groups with the following key stakeholders: group 1: COPD patients; group 2: clinicians; and group 3: rehabilitation specialists. Participants will be identified from the following settings: Chapidize Clinic in Tbilisi (COPD patients), Chapidze Emergency Cardiology Center (rehabilitation specialists) and primary and secondary care (clinicians). The focus groups will be carried out in the Chapidze Emergency Cardiology Center.

Participant timeline

Participants will be invited to take part in a single focus group session, which will last between 2.5 – 3.0.

Sample size

Each focus group will include 6-8 participants; this is considered as the optimum sample size for focus groups to enable effective and meaningful discussion to be generated among the participants (12), and achieve data saturation (13).

Recruitment

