Recruitment of COPD patients A sample of patients from the Chapidze Emergency Cardiology Center will be identified and invited (via telephone) to take part in the qualitative study. Those interested will be sent an invitation by e-mail which will include an invitation letter, information sheet and a reply slip to indicate their interest in participating. Participants will be contacted by the research team to arrange a date for the focus groups. Participants will receive a reminder call three days prior to the focus group.

Recruitment of healthcare professionals Primary care doctors and respiratory physicians, who are known to the Georgian Respiratory Association (GRA), and rehabilitation specialists based at Chapidze Emergency Cardiology Center, will be invited to take part in the qualitative study. These individuals will be initially contacted by the telephone, and/or through the information meetings (primary care doctors attend information meetings). Those interested will be sent an email, which will include an invitation letter, information sheet and a reply slip to indicate their interest in participating. Participants will receive a reminder call three days prior to the focus group.

Focus group sessions

Preparation for the focus group As there are currently no pulmonary rehabilitation (PR) services being offered in Georgia, both patients and the healthcare professionals will be familiarised with the PR programme, 2-weeks prior to the focus group sessions. A UK-based PR video will be provided to the participants; this will include PR exercises and education on the management of COPD. Handouts, containing details of other PR programme components in high income settings, will also be provided.

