 - b. Conducting the Incremental Shuttle Walking Test (ISWT): to be carried out twice; distance walked to be documented in meters; collect various measures pre and post each test (blood pressure, heart rate, oxygen saturations, Borg dyspnoea and RPE scores); record reason for cessation (e.g. breathless, dizziness, painful legs).
 - c. Self-administered participant questionnaire booklet: sociodemographic data (age, sex, ethnicity, education level, marital status, number of dependents; number of adults in the household; and employment); comorbidities; medications; level of dyspnoea (MRC score); smoking status; quality of life and disease specific questionnaires (EQ-5D-5L; St George's Respiratory Questionnaire [SGRQ]; and COPD Assessment Test [CAT]); anxiety and depression (GAD 7 and PHQ-9); self-reported physical activity levels (International Physical Activity Questionnaire [IPAQ]); and health service use (hospitalisations).
 - d. Measuring height and weight to calculate body mass index (BMI)
 - e. Saliva or urine sample to measure cotinine (nicotine levels)
- 4. Randomisation to the treatment or control group

The baseline assessment will be carried out by a member of the research team (exception: the ISWT will be carried out by the trained rehabilitation specialist(s)). The researcher will record all study data on CRFs to ensure standardised data collection/recording. On completion, the researcher will enter the data on to the secure REDcap electronic database.

Study assessment 2

At the end of the PR programme, participants will be invited to a second study assessment. This will include collecting similar data as the baseline assessment:

- 1. Conducting the ISWT (once), and collecting all pre and post-test measures (as detailed above), by the rehabilitation specialist
- 2. Self-administered participant questionnaire including the following: level of dyspnoea (MRC score); smoking status; quality of life and disease specific questionnaires (EQ-5D-5L; St George's Respiratory Questionnaire [SGRQ]; and COPD Assessment Test [CAT]); anxiety and depression (GAD 7 and PHQ-9); self-reported physical activity levels (International Physical Activity Questionnaire [IPAQ]); health service use (hospitalisations); patients costs (for those attending the PR programme); and injuries or health issues as a result of the PR programme.
- 3. Saliva or urine sample to measure cotinine (nicotine levels)

Study assessment 3

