Patients will be invited to attend a final follow-up assessment, after 6 months, to collect the following data:

- 1. The ISWT (once), and collecting all pre and post-test measures (as detailed above, and to carried out by a rehabilitation specialist)
- Self-administered participant questionnaire including the following: level of dyspnoea (MRC score); smoking status; quality of life and disease specific questionnaires (EQ-5D-5L; St George's Respiratory Questionnaire [SGRQ]; and COPD Assessment Test [CAT]); anxiety and depression (GAD 7 and PHQ-9); self-reported physical activity levels (International Physical Activity Questionnaire [IPAQ]); and health service use (hospitalisations)
- 3. Saliva or urine sample to measure cotinine (nicotine levels)

Study assessments 2 and 3 will be carried out by a member of the research team.

Process measures

To be able to assess the feasibility of delivering the PR intervention, the following will be measured:

- 1. Fidelity of delivery of the programme by the rehabilitation specialists: the aim will be to assess whether patients are achieving their prescribed exercise goals which have been set by the rehabilitation specialist. For this, a member of the research team will examine the following patient data over six PR sessions: attendance to all PR sessions (noting number of missed sessions); completion of all prescribed exercises; achieved all sets/repetitions/exercise duration prescribed for each exercise; achieved the recommended exertion score (Borg score); and exercise prescription review (changes by physios based on patient progress). This data will be completed by the patient at each visit, and stored in their research file.
- 2. Participant adherence to the intervention: number of sessions attended; completion of the PR programme; where sessions were carried out (home/clinic) and how many session within each setting; consistent achievement of prescribed goals (e.g. sets/reps/exertion); and education session attendance. This data will be extracted for the patient's research file.
- 3. Ability to carry out trial procedures: baseline data (% complete); follow-up rates (end of programme and 6-months); recruitment rate, and comparison of the characteristics with those who declined to take part; and completeness of data entry.
- 4. Reach: characteristics of the participants; ability to recruit the more socio-economically disadvantaged members of the population; and assessment of geographical reach

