- 5. Intervention acceptability rehabilitation specialists: to conduct qualitative interviews with staff who delivered the PR programme about training, confidence with delivery and how PR fits with the rest of health care for people with COPD.
- 6. Intervention acceptability and experience participants. To also conduct qualitative interviews with intervention group participants to explore their experience of the PR programme (n: 15-20). It is likely that all 30 intervention group participants will need to be invited for up to 20 to be interviewed. If acceptance rates are high then purposive sampling

will be used to ensure participants with a mix of socio-demographic characteristics, severity of COPD and differing levels of engagement with the PR programme. All participants who drop-out of the PR programme before completion will be invited to be interviewed to explore barriers to continuing with the PR programme. Semi-structured interview schedules based on the research literature, discussion within the team and input from PPI will be devised. All interviews will be recorded and transcribed verbatim. Reflective notes will be made following each interview.

Data management

Data will be collected on case report forms which will be kept by the [name] in a locked cabinet in a secure room at the Chapidze Emergency Cardiology Center, Tbilisi. The research team will enter data from case report forms into a bespoke REDCap online database. All electronic data held by the research team will be password protected and stored on encrypted study laptops. The research team will conduct monitoring visits during the recruitment period to ensure data are being collected, entered and stored according to pre-specified study working instructions.

Data analysis

Statistical methods

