Eligibility criteria- possibility that participants may be recruited that do not match the eligibility criteria (or include patients with exclusions criteria)	Recruit high risk patients, or those that do not have spirometry confirmed COPD.	Site training and use of an eligibility form will contain tick boxes containing individual statements regarding the inclusion/exclusion criteria. Spirometry will be carried out at the baseline visit to confirm COPD diagnosis.	Central monitoring will verify that eligibility was assessed prior to trial entry, on a proportion of patients

Possible Risk Design and methods	Describe the risk	Can the risks be reduced? What would you do?	How would you monitor the study to address concerns?
		Participants will be familiarised with the environment, and informed of safe areas as well as areas where there may be obstacles or equipment.	Adverse events will be documented in the patient file and on an incident log.
	Participants colliding with each other	Appropriate distances will be maintained between participants so that exercises can be carried out safely.	Rehabilitation specialists will receive additional training if safety issues are identified
Patient visits	Tripping over equipment Participants misusing equipment	Participants will be trained on how to use the equipment safely.	Patients will be re-trained on how to use equipment.
	Participant experiences a negative response to physical activity – excessive breathlessness or fatigue or dizziness	Rehabilitation specialists will carry out a pre- rehabilitation session with each participant to prescribe an individualised and safe exercise programme which is based on the patient's exercise capacity. Participants will be informed of how to respond if they experience a negative response to the exercise programme. A rehabilitation specialist will be available at each exercise session, and will observe all patients.	Rehabilitation specialists will re- assess on the patient's exercise prescription, and consider the need for changes. Researchers to assess incident logs to identify training needs of rehabilitation specialists.
Data collection methods	The risk of incomplete data is low as most CRFs will be completed face to face with the participant. There may be a small risk of incomplete data	The CRFs have been kept to a minimum and have been well reviewed, so complexity is reduced.	Early monitoring of data return may identify any issues

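### Both follow-up shuttle walk tests are assigned to the staff group that delivers pulmonary rehabilitation, and no rule separates tester from treater, so this effort-dependent outcome is at avoidable risk of assessor bias

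*Protocol*

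**What the plan says.** Under Data collection methods, Phase 2, the ISWT at Study assessment 2 (end of programme) is assigned as follows: "Conducting the ISWT (once), and collecting all pre and post-test measures (as detailed above), by the rehabilitation specialist". Study assessment 3 (6 months) does the same: "The ISWT (once), and collecting all pre and post-test measures (as detailed above, and to carried out by a rehabilitation specialist".

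The same staff group delivers the intervention. Process measures, item 1, is headed "Fidelity of delivery of the programme by the rehabilitation specialists", and item 5 plans, for rehabilitation specialists, "to conduct qualitative interviews with staff who delivered the PR programme". In the Appendix 2 risk assessment, the specialists hold a pre-rehabilitation session with each participant to set an individual exercise prescription, and "A rehabilitation specialist will be available at each exercise session, and will observe all patients".

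The text on Study assessment 3 closes with: "Study assessments 2 and 3 will be carried out by a member of the research team". The matching sentence for the baseline visit carves out the ISWT for the trained specialist(s). The follow-up sentence has no such exception.

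The protocol has no provision for masking assessors and no rule on who may test whom.

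**The concern.** The distance walked depends on effort. The intervention section treats ISWT performance as a maximum from which exercise intensity is set, and the case report form records why the patient stopped. The tester's encouragement and manner can affect how far a patient goes. Most other outcomes listed to inform a future trial are self-reported or biochemical, so the ISWT is where the tester's conduct matters most.

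The exposure differs between the arms. Before follow-up is complete, only PR participants can have been coached by a specialist, because the control group's session comes afterwards. A tester who has treated the patient is therefore possible in one arm only. The specialists also have an interest in the result, because fidelity is judged by whether patients reach goals that the specialists set.

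What is at stake is the between-arm ISWT difference, which the Outcome measures section lists among the results meant to inform a future effectiveness trial. A larger sample would not remove a tester effect.

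**Working it through.** **1. Who does what, set side by side (Protocol).**

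| Task | Staff | Place |
|---|---|---|
| Baseline ISWT | Trained rehabilitation specialist(s), as an exception to the research team's role | Study assessment 1 |
| End-of-programme ISWT | Rehabilitation specialist | Study assessment 2 |
| 6-month ISWT | Rehabilitation specialist | Study assessment 3 |
| Assessments 2 and 3 as a whole | Research team, no exception stated | End of Study assessment 3 |
| Prescribing and observing exercise | Rehabilitation specialists | Appendix 2 |
| Delivering PR | Rehabilitation specialists | Process measures, items 1 and 5 |

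Two things follow. The tester and the treater come from the same group, and nothing keeps them apart for a given patient. Also, the ISWT lines and the closing sentence on assessments 2 and 3 name different staff for the same task. The likely meaning is that the specialist runs the walk and the research team does the rest, but only the baseline text says so.

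**2. The plan's own figure.** 30 per arm × 2 arms = 60, as stated under Sample size. This figure does not depend on who tests, and the fix leaves it unchanged.

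**3. Scale, under assumptions.** The protocol gives no ISWT SD and no tester effect. Assume an SD of 100–150 m and a tester effect of 10–20 m in one arm:

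- smallest: 10 / 150 = 0.07 SD
- largest: 20 / 100 = 0.20 SD

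This range only restates its inputs. To place it against the trial's precision, take 30 per arm, no dropout and the normal approximation:

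- SE of the difference = √(2/30) = 0.258 SD
- 95% half-width = 1.96 × 0.258 = 0.51 SD
- coverage with bias b = Φ(1.96 − b/0.258) − Φ(−1.96 − b/0.258)
- b = 0.1 SD: 93%
- b = 0.2 SD: 88%

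In this trial a bias of that size would be hard to see against sampling error.

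**4. If the estimate were carried forward (conditional).** Suppose that the bias favours PR, that the true effect is 0.5 SD, and that a later trial is sized at 90% power and two-sided 5% on the biased estimate. Then n per arm = 2 × (1.96 + 1.28)² / d², rounded up:

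| Assumed bias | Estimate used, d | n per arm | Power at the true 0.5 SD |
|---|---|---|---|
| 0 | 0.5 SD | 85 | 90% |
| 0.1 SD | 0.6 SD | 59 | 78% |
| 0.2 SD | 0.7 SD | 43 | 64% |

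The protocol does not say that the ISWT will be used in this way. The table shows only what would follow if it were.

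**The case against.** The strongest reply has four parts.

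- **The trial is small in ambition.** It is an unpowered feasibility study, the ISWT is not among its feasibility outcomes, and HRQoL is the only clinical outcome that Statistical methods singles out for estimates by group with confidence intervals. This stands, and it limits the weight of the point. It does not remove it, because the ISWT is still collected to inform a future trial.
- **The text names a group, not a person.** A specialist who did not treat the patient may run the test. That is true, but nothing requires it.
- **The research team is not masked either.** It conducts the baseline visit that ends in randomisation, carries out the assessment that asks about PR costs and PR-related injuries, and reviews PR session data for fidelity. Nothing shows that it is trained in the ISWT. This stands: using that team removes the treating-staff interest but does not hide allocation.
- **There are partial checks.** Heart rate, oxygen saturation, and ratings of breathlessness and exertion are taken before and after each test and give some indication of effort. The listed reasons for stopping are the patient's own symptoms, and nothing says that the specialist decides when the walk ends. This is fair, but these measures do not show whether encouragement differed between arms.

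A reader might also infer that spare testers are plainly available, since Phase 1 says "rehabilitation specialists based at Chapidze Emergency Cardiology Center, will be invited to take part in the qualitative study" and "Each focus group will include 6-8 participants". The documents do not support that. Six to eight is a recruitment target for a discussion group, not a count of staff who will deliver PR or run the ISWT in Phase 2. The baseline text leaves open that there may be a single trained specialist.

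**Conclusion.** The point holds as a risk. As written, the plan lets the staff who coach the PR arm administer its only exercise-capacity outcome at both follow-ups, and the wording on who carries out those assessments is inconsistent. The change is worth making but is not critical to the trial's feasibility aims.

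Three stronger readings are tempting and should not be made. The documents do not show that the ISWT result is biased: direction and size are unknown, and 0.07–0.20 SD rests wholly on assumed inputs. They do not show that the SD would be distorted: a uniform shift in one arm leaves the within-arm SD unchanged, so the concern is with the estimated difference. Nor do they show that a masked tester is ready to hand.

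One related uncertainty remains. The Randomisation section places baseline measures after allocation, while Study assessment 1 lists randomisation last. If the former is followed, the baseline ISWT is exposed too, so those passages also need reconciling.

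**What to change.** In Study assessments 2 and 3, state that:

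- the ISWT is run by a member of existing staff who has not delivered PR to that participant. This would be another rehabilitation specialist or, if none is free, the research-team member already conducting the visit, after ISWT training;
- testers are chosen in the same way in both arms, so that type of tester does not become tied to allocation;
- the same scripted instructions and encouragement are used in both arms;
- the case report form records the tester's ID and whether the tester knew the allocation.

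Amend the closing sentence on assessments 2 and 3 so that it agrees with the ISWT lines, as the baseline text already does.

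The cost is some rostering or brief training and two extra fields on the form. No additional assessor is called for if either option can be staffed, and the sample size of 60 does not change. The limitation is that masking stays imperfect, because the research team may also know the allocation. The recorded fields would show how often that happened, which is itself useful when planning a future trial.

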A pre-rehabilitation one-to-one assessment will be booked at a time convenient for the patient. The aim of this assessment will be to orientate the patient to the PR intervention and tailor their exercise programme. For this, the ISWT, perceived exertion and breathlessness scale will be used to prescribe the intensity of the exercise component of the PR programme. Patients will be prescribed 65 - 85% of their maximal baseline ISWT performance (can be lower in deconditioned patients) (15).

The adapted PR programme will consist of two main components: exercise and education on the management of COPD. The description, content and frequency of these components will be determined during phase 1 of this project (cultural tailoring).

Control group

Participants randomised to the control group will be offered to attend a 2-3 hour educational session. This will be carried out by the rehabilitations specialists 6-months after study enrolment, once follow-up is complete.

Outcome measures

Data will be collected from patients at the end of the PR programme (6 - 8 weeks) and at sixmonths.

Feasibility study outcomes will include: delivery with fidelity, acceptability to participants, recruitment rate, follow-up rate at 6 months, adherence to intervention, ability to carry out trial procedures, feasibility of methods to measure costs of PR, other COPD-related health care utilisation and patient-incurred costs

Outcome measures to inform a future trial to evaluate clinical and cost effectiveness: HRQoL (SGRQ and EQ-5D-5L); exercise capacity measured by the ISWT; smoking status validated by cotinine; COPD Assessment Test (CAT); self-reported physical activity (IPAQ); self-efficacy; anxiety and depression

(PHQ-9 and GAD-7); self-reported exacerbations; health care utilisation including hospital admissions; and costs/resource use incurred by patients.

Participant timeline

Participants randomised to the intervention group will be invited to a baseline visit/one-to-one prerehabilitation assessment. The number of PR intervention visits per week, and the total length of the PR programme will determined after phase 1 of the project (focus group discussions).

Participants randomised to the control group will be invited to four visits: baseline visit, follow-up visits (end of programme and 6-months) and a 2-3 hour educational and exercise session (6 months).

Sample size

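### Fidelity of staff delivery is defined mainly by patient achievement from patient-completed records, so it largely overlaps adherence and leaves delivery of education unmeasured

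*Protocol*

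**What the plan says.** Under Outcome measures, the Protocol opens its list of feasibility outcomes with "delivery with fidelity, acceptability to participants, recruitment rate, follow-up rate at 6 months, adherence to intervention". Fidelity and adherence are therefore meant to be two different results.

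Process measures, item 1, names the first of them "Fidelity of delivery of the programme by the rehabilitation specialists" and then gives its purpose: "the aim will be to assess whether patients are achieving their prescribed exercise goals which have been set by the rehabilitation specialist". To do this, "a member of the research team will examine the following patient data over six PR sessions". Five indicators follow: attendance, exercises completed, prescribed sets/repetitions/duration reached, recommended Borg score reached, and review of the exercise prescription with changes by the physiotherapists. On the source, the item says "This data will be completed by the patient at each visit", and the records go into the patient's research file.

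Item 2, adherence, is taken from the same research file. It covers sessions attended, completion of the programme, where sessions took place, and "consistent achievement of prescribed goals (e.g. sets/reps/exertion); and education session attendance".

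The section on the intervention names two main components, exercise and education. It also gives a rule for the exercise intensity: "Patients will be prescribed 65 - 85% of their maximal baseline ISWT performance", with a stated exception that allows a lower level in deconditioned patients.

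**The concern.** The label of item 1 points to staff and its stated aim points to patients. A measure of delivery fidelity should record whether those running the programme did what the programme required. A measure of adherence should record whether participants took it up. If both are built from the same patient-completed records, the fidelity result carries little information beyond adherence.

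This matters here because Objective 2 is to assess the feasibility of delivering a tailored programme, in a country where the Protocol says no such service exists. Whether the specialists can deliver both components as planned is one of the things the trial is set up to learn. A participant who misses well-run sessions changes the attendance figure reported as fidelity. A programme whose education sessions leave out planned content changes none of the five figures.

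**Working it through.** No calculation of power, rate or precision applies, and the Protocol gives no figure to reproduce. The check sets the five indicators of item 1 against the adherence list in item 2 and against the two programme components.

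| Item 1 indicator | Whose action | Counterpart in item 2 |
|---|---|---|
| Attendance, with missed sessions noted | Patient | Number of sessions attended; programme completion |
| Prescribed exercises completed | Patient | Consistent achievement of goals |
| Sets/repetitions/duration reached | Patient | Consistent achievement of goals (sets and repetitions are named as examples) |
| Recommended Borg score reached | Patient | Consistent achievement of goals (exertion is named as an example) |
| Prescription review, with changes by physiotherapists | Staff | None |

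Counts:

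- Patient actions that item 2 also covers: 4 of 5 (4/5 = 80%).
- Staff actions found only under fidelity: 1 of 5 (1/5 = 20%).
- Indicators on delivery of education: 0 of 5.

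Source of the data: item 1 is completed by the patient at each visit and filed in the research file, and item 2 is extracted from that file. The research-team member in item 1 examines these records. The Protocol describes no observation of sessions for fidelity and no delivery record completed by the specialist.

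Education: the only education measure is in item 2, and it is patient attendance. It gives indirect evidence that a session took place and does not show which topics were covered.

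Initial prescription: no indicator compares the starting prescription with the ISWT-based rule in the intervention section, although the baseline ISWT distance is already recorded on the case report form.

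**The case against.** The programme is individually tailored, so comparing what a patient did with what was prescribed is a defensible, though incomplete, form of fidelity. The content and frequency of the programme are set only after phase 1, so a full delivery checklist could not be written yet. There is also related evidence. Staff are interviewed about training and confidence, 15 to 20 intervention participants about their experience, and everyone who drops out is invited to interview. The risk assessment in Appendix 2 has a specialist present and watching patients at each exercise session.

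Part of this stands. The detail can wait for phase 1, but the choice of construct is already written down and does not depend on it. The interviews come under acceptability, and the specialist's presence is a safety measure. Neither compares delivery with the plan.

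A reader might draw stronger conclusions, which the Protocol does not support:

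- *Fidelity is identical to adherence, or says nothing about staff.* The prescription review is a staff action that appears only under fidelity.
- *Easy goals would pass as high fidelity.* The Borg indicator and the prescription review partly guard against this, since goals set too low would tend to miss the recommended exertion.
- *Poor attendance would drag down a fidelity score.* No composite score is defined, and the indicators can be read separately.
- *The observation window contradicts itself.* "attendance to all PR sessions (noting number of missed sessions" can be read as all of the six sessions examined.
- *The trial could not explain a weak effect.* The Statistical methods section says the trial is not powered to detect a difference, and the research question is feasibility.

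**Conclusion.** The point holds as a misdefined feasibility measure. Item 1 is named for staff delivery but defined mostly by patient achievement. Four of its five indicators largely overlap adherence, one is a staff action, and none covers delivery of education. A fidelity result reported on this definition would mostly repeat adherence and give little direct evidence on whether the specialists delivered the programme.

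This rests on two readings. The first is that attending, completing exercises and reaching exertion targets are patient actions, even though staff encouragement influences them. The second is that item 2's achievement of prescribed goals covers exercises completed and duration reached, which its examples do not name. If those two indicators were treated as not covered, the overlap would be 2 of 5 in full (attendance and Borg score) and part of a third (sets and repetitions). The mismatch between label and aim, and the gap on education, would remain.

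The change should be made, but it is an inexpensive improvement. Nothing here affects randomisation, safety or the clinical outcome measures.

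**What to change.** Redefine item 1 on provider actions, using a short session record that the rehabilitation specialist completes and the research-team member already assigned to item 1 reviews. It should hold:

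- sessions held out of those scheduled;
- education topics delivered out of those in the programme fixed after phase 1;
- the initial prescription documented against the Protocol's own ISWT-based rule, with any use of its stated exception for deconditioned patients recorded, so that a permitted departure is not counted as a failure;
- prescription review done or not done.

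Report attendance and achievement of goals under adherence only, over all sessions. No patient data are lost by this.

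The definition can be amended now. The list of topics and the review points are filled in once phase 1 has fixed the programme. Both should be in place before the first session, because delivery that was not recorded is hard to reconstruct.

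The cost is a few minutes of staff recording per session, with no extra personnel. One limitation remains: specialists would be recording their own delivery, so the research team's review of the records should be kept.
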